#### **9.2.2 Safety Analysis**

All subjects entered into the study on C1D1 will be included in the safety analysis. The frequencies of AEs that occur through week 15 after the second dose of pembrolizumab by type, body system, severity and relationship to study drug will be summarized. SAEs (if any) will be described in detail. Potential association with study treatment will be assessed.

#### **9.2.3 Invasive Disease-Free Survival (IDFS)**

Secondary objective of IDFS will be evaluated by the Kaplan-Meier method. IDFS is defined as the time from completion of surgery to the first occurrence of the following events: invasive ipsilateral, local, regional, or distant recurrence, or death due to breast cancer.

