## STUDY SCHEMA

This is a prospective, phase Ib/II study of the preoperative combination of pembrolizumab (pembro) and radiation therapy (RT) in patients with operable breast cancer. Patients with newly diagnosed, Stage I-III breast cancer who are planned for breast-conserving surgery and adjuvant whole breast radiation therapy will be recruited into one of 2 cohorts as per their biomarker profile as depicted below. The TNBC cohort will have 50 subjects (10 TNBC subjects for phase Ib and 40 TNBC subjects for phase II) and the HR+ cohort will have 10 subjects. Enrollment will start with the phase Ib TNBC cohort. The trial will be conducted in a Bayesian design, wherein safety as assessed by lack of delay in standard of care treatment will be assessed after 3, 6, and 9 patients have initiated standard of care treatment in each cohort. Standard of care treatment is defined as breast-conserving surgery or initiation of neoadjuvant systemic chemotherapy. If the phase Ib TNBC trial meets a pre-specified safety endpoint, enrollment in

the phase II TNBC trial and HR+ cohort will take place.

Study treatment will consist of 2 doses of neoadjuvant pembro. The second dose will be given in combination with a RT boost. The primary objectives are: 1) to assess the feasibility of the preoperative combination of pembro and RT as defined by the number of patients who do not necessitate a delay in standard of care treatment, 2) to assess the change in tumor infiltrating lymphocyte (TIL) score with therapy. The secondary objectives are to describe the toxicity with preoperative pembro and RT up to 15 weeks after administration of pembrolizumab, to assess the invasive disease-free (iDFS) survival, and to assess the pathological complete response (pCR) rates.

- The first dose of pembro will be given on cycle 1, day 1 (C1D1). Each cycle will be 21 days. The second of pembro dose will be given on C2D1 (+/- 3 days).
- RT will be administered concurrently within one week of the second dose of pembro (C2D1 + 5 calendar days). 8Gy will be delivered in 3 fractions over 3 to 5 business days (for a total dose of 24Gy).
- Standard of care treatment, including breast-conserving surgery or additional neoadjuvant systemic therapy, will be pre-set to start 8 weeks after study enrollment (+/- 5 days).
- Research blood and stool will be obtained after consent up to C1D1. It will also be obtained on C2D1 (+/- 3 days) and at the time of initiation of standard of care treatment (+/- 5 days).

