### 2.2 Secondary Objectives

- 2.2.1 To describe the toxicity with preoperative pembrolizumab and RT up to 15 weeks after administration of pembrolizumab.
- 2.2.2 To assess invasive disease-free survival (iDFS) rates.
- 2.2.3 To assess the pathological complete response (pCR) rates.

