## 2.4 Endpoints

- **Primary Efficacy Endpoint: Feasibility**

Feasibility will be defined by the number of patients who do not necessitate a delay in standard of care treatment. Since the combination of pembrolizumab and RT has not been tested in the preoperative setting in patients with potentially curative disease, it is necessary to establish whether such preoperative treatment can be safely given without delaying curative-intent treatment.

- **Co-Primary Efficacy Endpoint: Change in TILs**

An increase in TILs is an indicator of immune system engagement. A lead in with pembrolizumab alone followed by the combination of pembrolizumab with RT will allow for serial assessment of TILs. This will establish the contribution of RT to the immune response generated by pembrolizumab.

- **Safety Evaluations**

Immune related adverse events that result from checkpoint blockade can occur weeks after the drugs are administered. Therefore, adverse events will be recorded up to 15 weeks after administration of pembrolizumab and radiation therapy and graded according to CTCAE, Version 4.03. Immune related adverse events will also be documented for up to 1-year post treatment. When considering if an adverse event is immune related, a general principle is that differential diagnoses should be diligently evaluated according to standard medical practice. Non-inflammatory etiologies should be considered.

- **iDFS**

iDFS will be defined as the time from completion of surgery to the first occurrence of the following events: invasive ipsilateral, local, regional, or distant recurrence, or death due to breast cancer.

- **pCR**

pCR will be defined as the absence of invasive disease in the breast and lymph nodes at the time of curative-intent surgery.

---

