#### **4.1.2 Women age 18 years or older**

- 4.1.3** Confirmed histologic diagnosis of invasive adenocarcinoma of the breast, and
- 4.1.4** ER, PR and HER2 testing (on outside or Cedars-Sinai biopsy report), and
- 4.1.5** High-risk, ER-positive and HER2-negative breast cancer patients. ER-positive disease is defined as ER $\geq$ 10%, any PR and HER2-negative by ASCO CAP guidelines. High-risk disease will be defined by the presence of at least 2 of the following 3 criteria: histologic grade II-III, Ki-67  $>$  20%, ER expression  $<$  75% by IHC)
- 4.1.6** TNBC patients (defined as ER $<$ 10%, PR $<$ 10%, HER2-neu 0-1+ by IHC or FISH-negative; or as per MD discretion)
- 4.1.7** Operable tumor measuring  $\geq$ 2 cm in maximal diameter as measured by any available standard of care imaging (examples include mammogram, breast ultrasound, breast MRI, CT) and/or by clinical exam
- 4.1.8** Any nodal status
- 4.1.9** Multifocal disease is permitted; largest focus must measure  $\geq$ 2 cm
- 4.1.10** Synchronous bilateral invasive breast cancer is permitted
- 4.1.11** No indication of distant metastases
- 4.1.12** Candidate for breast-conserving therapy
- 4.1.13** Tumor amenable to preoperative radiation therapy boost as determined by radiation oncologist
- 4.1.14** ECOG performance status score of 0 or 1
- 4.1.15** Screening laboratory values must meet the following criteria:
  - i. White blood cells (WBCs)  $\geq$  2000/ $\mu$ L
  - ii. Absolute neutrophil count (ANC)  $\geq$  1500/ $\mu$ L
  - iii. Platelets  $\geq$  100  $\times$  10 $^3$ / $\mu$ L
  - iv. Hemoglobin  $\geq$  9.0 g/dL
  - v. Serum creatinine  $\leq$  2 mg/dL (or glomerular filtration rate  $\geq$  40 ml/min)
  - vi. AST  $\leq$  2.5  $\times$  upper limit of normal (ULN)
  - vii. ALT  $\leq$  2.5  $\times$  ULN
  - viii. Total bilirubin within normal limits (except subjects with Gilbert's syndrome, who must have total bilirubin  $<$  3.0 mg/dL)
  - ix. INR  $\leq$  1.5  $\times$  ULN unless participant is receiving anticoagulant therapy as long as PT or aPTT is within therapeutic range of intended use of anticoagulant(s)
  - x. Negative HIV screening test
  - xi. Negative screening tests for Hepatitis B and Hepatitis C.

Patients with positive results that do not indicate true active or chronic infection may enroll after discussion and consensus agreement by the treating physician and principal investigator.

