#### 6.3.6 Survival Status

Survival status assessment and any documentation of recurrence (if possible) will be conducted every 6 months for up to 5 years following the end of treatment. Study staff will record survival status and recurrence via medical record review, phone call, or at standard clinical visits.

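### The iDFS event list omits contralateral invasive breast cancer but counts death from it, so iDFS is either unaffected or overstated

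*Combined protocol and SAP*

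**What the plan says.** **Definition.** Section 9.2.3 starts the clock at surgery ("IDFS is defined as the time from completion of surgery") and stops it at the "first occurrence of the following events: invasive ipsilateral, local, regional, or distant recurrence, or death due to breast cancer". Section 2.4 gives the same list: "invasive ipsilateral, local, regional, or distant recurrence, or death due to breast cancer". No other section adds to it.

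**Role and analysis.** iDFS is secondary objective 2.2.2 ("To assess invasive disease-free survival (iDFS) rates"). The whole analysis is one sentence in 9.2.3: "Secondary objective of IDFS will be evaluated by the Kaplan-Meier method". No test, benchmark, event target or decision rule is attached.

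**Size.** In the Study Schema, "The TNBC cohort will have 50 subjects" and the HR+ cohort 10, making 60 in all.

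**Data collected.** Section 6.3.6 says: "Survival status assessment and any documentation of recurrence (if possible) will be conducted every 6 months for up to 5 years". The long-term column of the Time and Events Table (6.4) marks survival status; the table has no row for a new primary cancer.

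**Related rules.** Inclusion criterion 4.1.10 reads "Synchronous bilateral invasive breast cancer is permitted". Section 6.5.8 allows a patient to be taken off treatment or study for a second cancer whose treatment would interfere with the study. No iDFS event or censoring rule goes with it.

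**The concern.** The endpoint's name promises freedom from invasive disease, yet the list follows only return of the treated cancer and death from breast cancer. A new invasive cancer in the opposite breast is not, in ordinary reading, an ipsilateral, local, regional or distant recurrence. The list is also at odds with itself: a death from that cancer is a failure, but the cancer that caused it is not.

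iDFS is the only stated long-term efficacy objective. The trial has a single regimen and no randomised control (5.3), so a lenient event list has no comparison arm in which it could cancel. Because 6.3.6 names survival and recurrence but not new breast primaries, the missing dates might not be on file if the definition were widened only at analysis.

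**Working it through.** The plan states no iDFS rate, event count or precision, so there is no figure to reproduce. The check is a reading of the rule, followed by a sizing under stated assumptions.

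**1. The rule applied to three constructed records** (months from surgery)

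| Record | Event under the written list |
|---|---|
| (a) Ipsilateral invasive recurrence at 18 | Event at 18 |
| (b) Contralateral invasive cancer at 18, alive at 60, no recurrence, still followed | None; counted as free of invasive disease at 60 |
| (c) Contralateral invasive cancer at 18, breast-cancer death at 48, nothing recorded between | Event at 48, which is 48 − 18 = 30 months after diagnosis |

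Records (b) and (c) are the extremes. A distant or regional recurrence recorded between 18 and 48 would bring the event in (c) forward. Removal under 6.5.8 could censor either woman near month 18.

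**2. Direction.** Time to the first event on a shorter list cannot be less than time to the first event on a longer list containing it. The probability of being event-free under the written list is therefore equal to or above the probability under the wider list. Censoring at the contralateral diagnosis does not repair this, since it replaces a failure by a loss to follow-up.

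One qualification applies to a single observed curve. If a contralateral patient later has a listed event, and others are censored in between, the postponed event falls on a smaller risk set. With three women (one as in record (c), one censored at 30, one followed to 60), the wider list gives 2/3 = 66.7% after month 18 and the written list gives 1/2 = 50% after month 48. So the one-way statement concerns the probability being estimated. It is exact for the curve itself with complete follow-up.

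**3. Size per case.** With complete follow-up, an omitted first event raises the curve by 1/N until a listed event occurs in that woman: 1/60 = 1.67 points, or 1/50 = 2.0 points in the TNBC cohort.

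**4. Size for an assumed rate.** The documents give no contralateral rate. Assume a constant hazard c of 0.3% to 1.0% per year, independent of the listed events, and a 5-year iDFS under the written list (S) of 70% to 90%.

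Overstatement at 5 years = S − S·exp(−5c) = S·[1 − exp(−5c)].

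| c per year | 1 − exp(−5c) | S = 70% | S = 80% | S = 90% |
|---|---|---|---|---|
| 0.3% | 0.0149 | 1.04 | 1.19 | 1.34 |
| 0.5% | 0.0247 | 1.73 | 1.98 | 2.22 |
| 1.0% | 0.0488 | 3.41 | 3.90 | 4.39 |

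The last three columns are percentage points.

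**5. Missed first events among 60 women.** With λ = −ln(S)/5, the expected number is 60·c/(λ+c)·[1 − exp(−5(λ+c))].

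- c = 0.3%: 0.75 (S = 70%) to 0.85 (S = 90%)
- c = 1.0%: 2.46 (S = 70%) to 2.78 (S = 90%)

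Listed events over the same range number 60·(1 − S) = 18 down to 6. At c = 0.3% the chance of no missed event is (1 − 0.75/60)^60 = 47% down to (1 − 0.85/60)^60 = 42%.

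**6. Against sampling error.** The binomial 95% half-width at N=60 with complete follow-up is 1.96·√[S(1 − S)/60]: 7.6 points at S = 90% and 11.6 at S = 70%.

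**The case against.** The best defence is that the definition is explicit, appears twice in the same terms, and follows the treated cancer and breast-cancer death. It cites reference 60, but the reference list as supplied ends at 56, so agreement with its source cannot be tested. That is fair, and nothing here rests on an outside standard. What remains is the conflict with the endpoint's own name and the counting of a death without the disease that led to it.

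Several stronger readings are tempting, and the documents do not support them.

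- **That such a woman stays event-free until she dies.** A later distant or regional recurrence would count first, and 6.3.6 looks for recurrence every 6 months. Removal under 6.5.8 might censor her, but that is discretionary, and 6.6 keeps patients with another malignancy under monitoring. The outcome is undefined rather than fixed.
- **That the curve is in fact too high.** This needs at least one contralateral cancer as a first event. At the low assumed rate there is a 42% to 47% chance of none among 60 women.
- **That recurrence in the second breast goes uncounted in women enrolled with bilateral cancer.** The list has local recurrence as well as ipsilateral, and local plausibly covers either treated breast. A clarifying sentence is useful, but no defect is shown.
- **That the bias could be much larger.** Higher rates, such as 2% per year, have no basis in the documents.

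The sizing also leans high. It assumes 60 women all followed for 5 years from surgery. Follow-up runs for at most 5 years from the end of treatment, recurrence is recorded only where possible, and Phase II may stop after 22 patients (9.1). The assumed bias is also smaller than the sampling error. These points limit the importance of the omission. They do not remove it, because sampling error has no preferred direction and this does.

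**Conclusion.** The point stands as a correctable fault in a secondary endpoint. Both iDFS definitions omit contralateral invasive breast cancer while counting death from it, and the estimated iDFS probability is unchanged or too high as a result.

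The per-case size, 1.67 points at N=60 or 2.0 at N=50, needs only complete follow-up. The range of about 1.0 to 4.4 points rests on assumed constant, independent hazards, a contralateral rate of 0.3% to 1.0% per year and a 5-year iDFS of 70% to 90%; none of these comes from the documents.

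A reader might infer that the trial's conclusions are at risk. They are not: iDFS carries no test or decision rule, so no sample size, alpha or go/no-go decision depends on it.

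**What to change.** 1. In 2.4 and 9.2.3, add contralateral invasive breast cancer to the event list, with the event dated at diagnosis.
2. In 6.3.6, have the existing 6-monthly review record contralateral invasive breast cancer and its date alongside recurrence.
3. As a clarification only, state that for women enrolled with synchronous bilateral cancer, invasive recurrence in either breast is an event.

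The cost is one phrase in two sections, one clarifying sentence and one item in a chart review or phone call that already takes place. No visits, tests or patients are added. The downside is a slightly lower reported iDFS if such cancers occur. The change is best made before iDFS data are examined, so that the event list cannot appear to have been chosen in the light of the events.

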### 3.0 STUDY DESIGN

#### ***Study Design***

This is a prospective, single-institution, Phase Ib/II study of the preoperative combination of pembrolizumab (pembro) and radiation therapy (RT) in patients with operable breast cancer (TNBC). The two cohorts will consist of 50 TNBC and 10 HR+ women each. Enrollment will start with the Phase Ib TNBC safety cohort. The trial will be conducted in a Bayesian design, wherein safety as assessed by lack of delay in standard of care treatment will be assessed after 3, 6, and 10 patients have initiated standard of care treatment. If at least 80% of the first 10 subjects in the TNBC cohort proceed with standard of care therapy without delay, the combination will be deemed safe in the cohort, and enrollment in the HR+ cohort, as well as continued enrollment in the TNBC cohort (40 subjects), will occur at that time.

Each cohort will be evaluated for delay in curative-intent standard of care treatment every time 3 patients complete study therapy and undergo standard of care treatment. At each of those timepoints, if the posterior probability that a patient experiences a delay in standard of care treatment exceeds 20%, the cohort will stop enrollment. In Bayesian statistics, the posterior probability of a random event or an uncertain proposition is the conditional probability that is assigned after the relevant evidence or background is taken into account. This design will assure that a cohort does not continue enrollment if early delays in standard of care treatment are seen. Enrollment will be carried out continuously and will not be stopped in order to evaluate the posterior probability of a delay. However, the number of patients undergoing assessment for a possible delay simultaneously will not exceed four in each of the 2 cohorts.

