## 9.2 Data Sets Analyzed

### Data Analyses/Study Endpoints

#### 9.2.1 Efficacy Analysis

The primary analysis will be based on an intention-to-treat approach and will include all subjects who receive a dose of study drug.

Phase Ib:

The primary efficacy endpoint will be feasibility as defined by the number of patients who do not necessitate a delay in standard of care treatment. Let  $P_d$  be the true probability that a patient experiences a delay. The trial will stop if there is statistical evidence that  $P_d$  exceeds 20%. We will use a Bayesian sequential design by checking whether  $P_d$  exceeds this threshold value after 3, 6, 9, ... patients are evaluable for feasibility. The decision rule is to stop the trial if the posterior probability that  $P_d$  exceeds 0.20 is 0.95 or more;  $P(P_d > 0.2 | \text{data}) > 0.95$ . A non-informative prior distribution for  $P_d$  will be used. Table 9.2.1 gives the stopping rules for the design at each look and column 2 gives the maximum number of patients with delay in order for the trial to proceed. Stopping rules will also apply for any patients with clinical progression of disease during study treatment, although this is expected to be uncommon. For example, if 4 or more delays in treatment are observed after enrolling 6 patients, the trial stops. The third column gives the probability of stopping the trial when in fact, the true  $P_d = 0.20$ . This is the equivalent of the Bayesian type I error probability. The target type I error probability was set at 0.05.

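### iDFS counts only deaths due to breast cancer, so other post-surgical deaths can only be censored and the rate is too high or at best unchanged; it also describes operated patients only and should say so

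*Combined protocol and SAP*

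**What the plan says.** The secondary objective in section 2.2 is "To assess invasive disease-free survival (iDFS) rates". Section 2.4 sets the clock: "iDFS will be defined as the time from completion of surgery to the first occurrence of the following events". Section 9.2.3 repeats that origin and gives the same event list: "invasive ipsilateral, local, regional, or distant recurrence, or death due to breast cancer". The only analysis statement is that the "Secondary objective of IDFS will be evaluated by the Kaplan-Meier method".

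Neither section gives a censoring rule, a competing-risk method, an analysis set for iDFS, or a rule for patients who progress, die or never have surgery. No iDFS target, event count or significance level is stated anywhere.

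On follow-up, section 6.3.6 says: "Survival status assessment and any documentation of recurrence (if possible) will be conducted every 6 months for up to 5 years". It lists survival status and recurrence. It does not mention cause of death, and the documents describe no procedure for attributing it.

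**The concern.** Disease-free survival is normally read as the chance of being alive and free of invasive disease. The event list does not deliver that, because a patient who dies of something other than breast cancer leaves the Kaplan-Meier risk set without counting as a failure. The curve then treats her as if her later relapse experience would have matched that of the patients still alive.

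The affected deaths include those a reader would most want counted after an experimental immunotherapy and radiation regimen given with curative intent. Section 5.4 notes that immune-related events may appear several months after the last dose, which can be after surgery.

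The time origin raises a second, smaller matter of interpretation. All pembrolizumab and study radiation come before time zero. So does chemotherapy when it is given before surgery, usually in weeks 7 to 25 according to section 6.3.2. A patient who never reaches surgery has no iDFS time at all, and nothing in the plan tells the reader how many such patients there were.

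At stake are the reported iDFS rate and any informal comparison of it with outside data.

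**Working it through.** **No figure to reproduce.** The plan states no iDFS rate, so this is a check of logic with illustrative sizes.

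**Step 1: where each type of failure goes under the definition as written.**
- Invasive recurrence after surgery: event.
- Breast-cancer death after surgery: event.
- Any other death after surgery: not an event. With Kaplan-Meier and no competing-risk rule, the only remaining treatment is censoring. The text does not say this; it follows from the event list and the method.
- Progression or death before surgery: before time zero, so outside the analysis. Such a patient is excluded, not censored.

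**Step 2: weight of one omitted death, with complete follow-up.** Cohort sizes come from Study Design in section 3.0: "The two cohorts will consist of 50 TNBC and 10 HR+ women each". Let N patients have surgery, R have recurrence (assumed) and one die of another cause. For illustration, all 50 or all 10 are taken to have surgery.
- Counting all deaths: (N − R − 1)/N.
- As written, if the death comes after all recurrences: 1 − R/N. The gap is 1/N.
- As written, if it comes before all recurrences: 1 − R/(N − 1). The gap is smaller than 1/N whenever R > 0.

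| N | R (assumed) | As written, death last | As written, death first | All-cause | Gap |
|---|---|---|---|---|---|
| 50 | 10 | 40/50 = 80.0% | 39/49 = 79.6% | 39/50 = 78.0% | 1.6 to 2.0 points |
| 10 | 2 | 8/10 = 80.0% | 7/9 = 77.8% | 7/10 = 70.0% | 7.8 to 10.0 points |

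The ceiling is therefore 1/50 = 2 points and 1/10 = 10 points per death. It rests on complete follow-up. If many patients have already been censored for short follow-up, one late death carries S/n, where S is the current estimate and n the number still at risk, and this can exceed 1/N.

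**Step 3: effect of the death restriction alone over an assumed range.** Assume constant hazards, a breast-cancer event risk of 20% or 30% over the horizon, and a risk q of other death over the same horizon. As written, S = 1 − risk. Counting all deaths, S = (1 − risk)(1 − q).

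| Breast-cancer event risk | q | As written | All-cause | Gap |
|---|---|---|---|---|
| 20% | 0% | 80.0% | 80.0% | 0 |
| 20% | 2% | 80.0% | 78.4% | 1.6 points |
| 20% | 6% | 80.0% | 75.2% | 4.8 points |
| 30% | 2% | 70.0% | 68.6% | 1.4 points |
| 30% | 6% | 70.0% | 65.8% | 4.2 points |

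The gap is never negative.

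**Step 4: how iDFS differs from an all-dosed endpoint.** Add an assumed proportion p of dosed patients who fail before surgery: event-free survival = (1 − p)(1 − risk)(1 − q). This ignores the difference in clock time before surgery. With p = q = 2%, it is 0.98 × 0.80 × 0.98 = 76.8% against 80.0%, or 0.98 × 0.70 × 0.98 = 67.2% against 70.0%. This gap of about 3 points is a difference between two endpoints; only the part from q is a fault in iDFS itself.

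**The case against.** **The surgical origin is legitimate.** A patient whose tumour is still in place is not yet disease-free, so starting a disease-free interval at surgery is coherent. Counting failures from C1D1 gives event-free survival, which is a different endpoint. A reader might infer that iDFS breaks the plan's own intention-to-treat rule, since section 9.2.1 says the analysis "will include all subjects who receive a dose of study drug". That sentence covers the primary analysis, and section 9.2.3 never claims to describe everyone dosed. This objection stands. It leaves a need for labelling and a supplementary estimate, not a reason to replace the origin.

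**Harm is recorded elsewhere.** A reader might also infer that toxic deaths and pre-surgical progression disappear from the trial. They do not. Section 9.2.2 includes all subjects entered on C1D1 and describes SAEs in detail. Section 7.1.2 makes death an SAE, and section 7.6.2.1 sends on-study deaths to the DSMC within 24 hours unless expected. Immune-related events are collected to one year, delay to standard of care is a primary endpoint, and section 9.2.1 brings progression during study treatment under the stopping rules. What remains is narrower: overall survival is not an objective and has no analysis in section 9, so a death from another cause enters no planned time-to-event estimate.

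**The size may be small.** There may be no such deaths, and the standard error of an 80% rate in 50 patients is √(0.8 × 0.2/50) = 5.7 points. That is fair, and it bears on priority. It does not justify an event list that can err in only one direction when the correction is a change of wording.

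**Conclusion.** The concern holds for the event list. Restricting deaths to breast cancer, with Kaplan-Meier and no competing-risk rule, makes the estimate too high or at best unchanged as a disease-free survival rate. With complete follow-up, each omitted death is worth at most about 2 points at N = 50 and 10 points at N = 10, and the effect is zero if none occurs. Recurrence and other-death rates are assumptions, because the documents give none.

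The time origin is not an error. It limits iDFS to operated patients, and the plan should say so.

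A larger figure is tempting: two pre-surgical failures plus one other death among 50 would be 3/50 = 6 points. The documents do not support it. The events are hypothetical, section 9.2.1 expects progression during study treatment to be uncommon, and the sum mixes two endpoints. It is also a ceiling reached only with no recurrences. With 48 operated and 10 assumed recurrences, iDFS as written is 1 − 10/47 to 1 − 10/48 = 78.7% to 79.2%, against 37/50 = 74.0% for event-free survival in all dosed patients, a gap of 4.7 to 5.2 points. With 15 recurrences the gap is 4.1 to 4.8 points.

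iDFS is secondary, single-arm and descriptive. Sample size, type I error, stopping rules and the pCR decision are unaffected.

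**What to change.** 1. In sections 2.4 and 9.2.3, replace death due to breast cancer with death from any cause, and state the censoring rule (for example, last date known alive and free of recurrence).
2. State in both sections that iDFS describes patients who complete surgery. Report how many dosed patients never reach surgery, by cohort and with reasons.
3. Add as a supplementary estimate event-free survival from C1D1 in all dosed patients. Before surgery, count progression precluding surgery and death from any cause as events; after surgery, use the corrected iDFS events.

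**Cost.** Item 1 is wording, and the survival status it needs is already collected for up to 5 years under section 6.3.6. The reported rate may be slightly lower. Items 2 and 3 need a recorded reason and date for each patient who does not reach surgery. The Time and Events Table in section 6.4 has no dedicated assessment of progression or operability before surgery, so this should be captured on the case report form. If the breast-cancer-death version is also kept for comparison, cause of death must still be recorded, so no saving there should be claimed.
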